3.1 Intensive case management measures

The following measures would be applied to patients with a high risk of readmission or who have experienced early readmission. In addition to the measures from the previous levels, the following would be incorporated:

-Schedule at least three follow-up appointments: one, in this case, in-person, with a psychiatrist from the MHHU within 24 hours post-discharge, and two at the Community Mental Health Unit: the first within 7 days and the second between days 21 and 30.

-If the patient has a Severe Mental Disorder, schedule two nursing visits: one during the hospitalization and one in the first week post-discharge. The latter will preferably be conducted at the patient's home.

-If the patient has documented medication non-adherence, consider depot medication based on clinical characteristics.

-All readmissions and patients at high risk of readmission will be assigned a case management figure who will develop a follow-up program for each patient and manage all their appointments during the first month post-discharge. This includes reminding patients of appointments 24 hours in advance, reengaging patients in case of non-attendance, and coordinating with reference facilities.

3.2 Post-Discharge Psychotherapeutic Recovery Support Program

For application to patients at high risk of early readmission who meet the inclusion criteria. The proposed psychotherapeutic intervention is considered as an adjunct to the standard treatment received by patients, as well as to the intensive case management measures proposed. It consists of a multicomponent group psychotherapeutic intervention from a rehabilitative and recovery-oriented perspective (10) This intervention will be structured into 20 sessions, each lasting 90 minutes, held weekly in an open format. It will be directed by two cotherapy professionals. The group will consist of a maximum of 12 participants, who may join at different times.

The intervention program includes different areas of work that are developed in a transversal way throughout the 20 sessions, following an open and flexible semi-structured format. Each area of work was included based on the available evidence regarding the effectiveness of psychosocial and psychotherapeutic interventions collected in scientific literature, Clinical Practice Guidelines, and the Integrated Care Process in Severe Mental Disorder of the Andalusian Health Service (8–12). The contents addressed by the Post-discharge Recovery Support Psychotherapeutic Program can be grouped around the following areas:

- Initial Phase: Introduction. Explanation of the framework and group rules. Addressing group objectives. Exploring personal expectations and identifying needs. Initiating therapeutic rapport and fostering group cohesion. These aspects will be addressed throughout the intervention and will be more evident during the welcoming of new group participants.
- Interpersonal Management: With the aim of promoting interpersonal functioning and independence, as well as adaptation to the community, dysfunctional relationship patterns will be addressed, which will be manifested in the group's own functioning. Both social perception skills or reception, social cognition or processing skills, and behavioral response or expression skills will be addressed.
- Problem Solving: This area of work aims to establish a link between symptoms and practical difficulties in their immediate context. Identifying and breaking down the problem, setting achievable goals, generating solutions, implementing them, and evaluating the results will be some of the skills to work on.

- Symptom Management and Coping Resources: This involves promoting recognition of the clinical condition, facilitating awareness about the origin of distress, its course, and typical ways of expression, fostering self-awareness and self-management. The relationship with the symptom, its acceptance, and pharmacological management will be addressed, along with recognition of prodromes, self-care habits, and crisis management.
- Family intervention: Four multi-family sessions will be carried out on a monthly basis in an integrated manner. They will be mainly based on the optimization of communication strategies in the family environment and management of crisis situations.
- Values orientation and commitment to meaningful activities: The therapeutic approach is focused on achieving greater subjective well-being and attaining a more satisfying and meaningful life, always from a recovery-oriented and person-centered model.
- Relapse prevention: Anticipation of possible scenarios, detection of potential risks and implementation of effective coping strategies. Strategies aimed at enhancing self-control, self-efficacy and self-determination, through the joint development of safety plans and the enhancement of personal strengths.

Other aspects that will be addressed throughout the therapeutic process include emphasis on the therapeutic bond, group cohesion, strengthening social and family ties, peer support, and learning in the here and now of the group reality.

Control group

To assess the effectiveness of the Multicomponent Discharge Transition Program, users from Málaga East Axarquía Hospital and North Málaga Health Management Area will be employed as the control group. Participants in the control group will continue with their usual treatment.

Additionally, users from the Mental Health Management Unit of Regional Hospital of Málaga who were admitted the previous year and thus did not participate in the intervention program will also be used as a control group.

- **Participants and recruitment**

For the development of the present study, data from all hospital admission episodes at MHHU during the 12 months following the implementation of the Discharge Transition Intervention Program will be considered. Similarly, data from all users who have experienced any hospital admission episodes at UHSM in the year prior to the intervention will also be utilized.

The experimental group, to which the Discharge Transition Intervention Program will be applied, will consist of users whose Community Mental Health Units (CMHU) are affiliated with the Regional Hospital of Málaga. Users belonging to other hospitals in the province will be excluded from the intervention program and will form part of the control group.

Participants included in the Post-Discharge Group Psychotherapy Support Recovery Program will be those at high risk or with an early rehospitalization already occurred, who also meet the inclusion criteria. The relevance of their inclusion will be assessed through a clinical interview by the Specialist in Clinical Psychology in charge of the program, following these criteria.

Inclusion criteria:

- Be of legal age.
- Speak spanish fluently.
- Have had recent admission to the MHHU of the Regional Hospital of Málaga and a score considered as "High Risk" on the Early Rehospitalization Risk Scale or have experienced an early rehospitalization.
- Belong to the Clinical Management Unit of Mental Health of the RUH of Málaga.
- Have sufficient cognitive capacity to understand the rules and contents of the group intervention.

Exclusion criteria:

- Individuals whose primary diagnosis is a Mental and Behavioral Disorder due to psychoactive substance use.
- Moderate or severe intellectual disability.
- Clinical Management Unit belonging to a hospital other than the RUH of Málaga.
- Lack of commitment to attending sessions or complying with group rules.

- **Study variables**

Main outcome variables

The main outcome variable will be the risk of early reentry of the experimental group compared to the control group, which did not follow the intervention.

Secondary outcome variables

The risk of early rehospitalization of the admission episodes from the experimental group will be compared to the risk of early rehospitalization of admission episodes from the previous year.

Frequent rehospitalization will be assessed as having undergone at least two readmissions within a 6-month follow-up period. The risk of frequent rehospitalization will be considered as a secondary variable.

In order to assess the effectiveness of the Recovery Support Psychotherapeutic Program, pre- and post-intervention scales will be administered to all participants to take into account other psychological and clinical variables. This evaluation will be conducted by blinded evaluators before the program begins and upon its completion, after the last session. The instruments to be used are as follows:

-Core Om (13,14): It is a self-report questionnaire composed of 34 items that allows for a brief assessment of the patient's status, widely used for evaluating therapeutic change based on four dimensions: Subjective well-being, Problems/Symptoms, General functioning, and Risk scale. The questionnaire items are scored on a Likert scale from 0-4. It is a valid and reliable instrument in its Spanish version.

- The Duke Social Support Questionnaire (Duke-unk-11) (15,16), assesses the perceived degree of social support. It is a self-administered questionnaire consisting of 11 items and a Likert-type response scale (1-5).

- The Personal and Social Performance Scale (PSP) (17,18), It is a hetero-applied and very brief instrument that allows quantifying changes in the functional recovery of patients in the following areas: a) self-care; b) usual social activities, including work and study; c) personal and social relationships; and d) disturbing and aggressive behaviors. The result on the scale is established by assigning to each of the areas a severity level. The total score ranges from 0 to 100.

- Recovery Process Questionnaire (QPR-15-SP) (19) is a self-reported questionnaire used to assess progress in measures of recovery linked to overall psychological well-being, personal achievements, quality of life, and empowerment. It consists of 15 items on a Likert scale from 0 to 4, with a high score indicating recovery. It has adequate reliability and validity indices and has been psychometrically adapted and validated in the Spanish population (20).
- Client's Assessment of Treatment (CAT). This scale evaluates patient satisfaction with hospital treatment, and in this study, it will be adapted to extend this measure to the overall mental health treatment received. Users rate each item on a scale from 0 to 10 (21,22).

- **Data analysis**

In the analysis for the creation of the early rehospitalization risk scale, a univariate logistic regression analysis will be used. For the final selection of factors, a forward stepwise multivariate analysis will be performed, introducing variables with greater statistical significance. Finally, a scale will be developed to measure the risk of early rehospitalization in each admission episode, whose sensitivity and specificity will be tested beforehand using a receiver operating characteristic (ROC) curve. The construction of the scale will follow the procedure outlined in detail in Sullivan et al. (23).

To evaluate the differences between the intervention group and the control groups, a univariate and multivariate mixed logistic regression analysis will be conducted, introducing potential confounding variables (unit occupancy, age, sex, and the variables used in the scale for estimating the risk of early rehospitalization). To assess potential differences in Core Om, Duke-unk-11, PSP, and QPR among patients participating in the Post-Discharge Recovery Support Psychotherapy Program, the paired Student's t-test for repeated measures or the non-parametric Wilcoxon signed-rank test for a single sample will be used.

DISCUSSION

The present research study aims to analyze the risk factors for early rehospitalization of patients discharged from a short-term psychiatric hospitalization unit. Based on this information, the goal is to stratify the risk and direct more intensive therapeutic measures to those individuals with a higher likelihood of rehospitalization to reduce early rehospitalization rates.

Thus, determining the risk of psychiatric rehospitalization for individual patients is a critical step in efforts to address the potentially avoidable high rate of this negative outcome, as highlighted in the READMIT study (4). This study conducted in Canada succeeded in providing a framework to identify patients at high risk of rehospitalization through the development of a prognostic index with moderate discriminative capacity.

One of the main strengths of our study is that it will be conducted in a real-world context, and the instrument to be used for patient stratification will be developed in the same population where it will subsequently be applied, reducing the possibility of cultural factors or context-specific factors biasing the validity of the risk scale. Additionally, the individuals involved in the care of hospitalized patients will work directly on this instrument and subsequently on the intervention to be developed, which will consist of multiple components.

Among the challenges of the study are being able to fulfill all the measures outlined in the intervention program, as external factors may condition it: shortage of hospital beds, premature discharges or voluntary discharges, staffing deficits, lack of community resources, etc. Additionally, many factors associated with early rehospitalization may be difficult to address within the program itself: substance abuse, homelessness, difficulties associated with group work, cognitive deficits, heterogeneity of participating subjects, etc.

One of the major limitations of the study is that it will only be conducted in one inpatient unit, so generalization of the results to other settings will be problematic. As reflected in previous studies, such as the one cited above, its findings have not been able to effectively discriminate potentially readmitting patients in subsequent studies conducted with different populations (24). This tells us about the complexity of the phenomenon of early readmission, an event that is difficult to predict, multicausal and involves factors that require a complex approach (25).

Finally, an important aspect is that the treatment allocation is not randomized, which may introduce biases that will be addressed by using two control groups. However, there may potentially be confounding variables that will be considered in the analysis. Given these limitations, if this study yields satisfactory results, a likely future direction could be to develop a randomized, multicenter clinical trial at the regional or state level.

LIST OF ABBREVIATIONS

CAT: Client's Assessment of Treatment
CMHU: Community Mental Health Unit
CPG: Clinical Practice Guidelines
CTI: Critical Time Interventions
MHHU: Mental Health Hospitalization Unit
PDC: Provincial Drug Dependency Center
PSP: Personal and Social Performance Scale
QPR: Recovery Process Questionnaire
RUH: Regional University Hospital
TDM: Transitional Discharge Model

DECLARATIONS

Ethics approval and consent to participate

The protocol of the current study has been submitted and approved by the Provincial Research Ethics Committee of Málaga, with approval number:

For the study of risk factors and the development of the early rehospitalization risk assessment scale, as well as for comparing the rehospitalization risk between study groups, retrospective clinical data recorded in the unit's electronic records will be used, and obtaining informed consent has not been deemed necessary. Prior to participating in group psychotherapeutic intervention, participants will sign informed consent before commencement.

The study will be conducted according to national and international standards outlined in the Declaration of Helsinki and Kyoto. Confidentiality of the subjects included in the study will be ensured in accordance with the provisions of Organic Law 3/2018, of December 5, on the Protection of Personal Data and guarantee of digital rights, as well as European Regulation 2016/679 regarding the protection of individuals with regard to the processing of personal data and the free movement of such data.

Consent for publication

Not applicable.

Availability of data and materials

The datasets used and analysed during the current study are available from the corresponding author on reasonable request.

Competing interests

The authors declare that they have no competing interests.

Funding

[name] and [name] have received a “Río Hortega” contract grant from the Ministry of Science and Innovation of Spain (Carlos III Health Institute). Instituto de Salud Carlos III, Río Hortega Grant CM22/00232, [name]; Río Hortega Grant CM21/00255, [name].

Authors' contributions

[name]: Participated in study design, acquisition of data and was major contributor in writing this manuscript; [name]: participated in the conceptualization and revision of the manuscript; [name]: contributed in the conceptualization and revision of the manuscript; [name]: Participated in study design, provided access to the data and reviewed the manuscript. [name]: Participated in conceptualization and revision of the manuscript; [name]: Contributed to study and data analysis design and in the writing and revision of the manuscript. [name]: Participated in conceptualization, study design, writing and revision of the manuscript. All authors read and approved the final version.

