- To assess whether a Multicomponent Discharge Transition Intervention reduces the risk of early readmission compared to a control group following standard treatment.

- Secondary**

- To check whether the risk of early readmission is reduced with respect to the previous year in the experimental group and in the control group.

- To check whether early readmission rates are reduced in the experimental group compared with the control group and with respect to readmission rates in the previous year.

- Identify risk factors that are associated with early readmissions.

- To test whether a scale for estimating the risk of early readmission has adequate psychometric characteristics for such estimation.

- To test whether a Post-Discharge Recovery Support Psychotherapy Group improves outcome on measures of recovery, functioning, subjective well-being, social support, and satisfaction with mental health treatment in patients at high risk of early readmission.

- To test whether the Transition to Discharge intervention also reduces the risk of frequent readmission (revolving door).

- **Design**

The present study is a quasi-experimental cluster clinical trial aimed at assessing the efficacy of a multicomponent discharge transition program for the reduction of early readmissions in a MHHU. The development of this study consists of two distinct parts or elements:

To carry out the main objective, a quasi-experimental design with a control group will be used, and within the intervention, an early readmission risk assessment scale will be created to categorize patients into different risk levels.

In addition, a study will be conducted to assess the predictive value and validity of the early readmission risk rating scale and to study the risk factors for early readmission.

- **Setting**

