The intervention program is based on the Discharge Transition Model for the prevention of hospital readmission in Mental Health. For its development, a multidisciplinary readmission commission was established, comprised of professionals from various categories and from different Mental Health facilities. The aim was to address this issue in detail and actively participate in the review of available evidence and decision-making regarding the development and implementation of the current program.

This is a multicomponent program that initially involves the development of a scale to assess the risk of readmission for each patient, followed by its systematic application. This allows for stratification of patients according to their risk of early readmission and adaptation of the intervention to the needs of each risk level. The intervention includes elements aimed at promoting continuity of care after discharge, transitioning back to the community setting, as well as elements aimed at enhancing personal and emotional resources through psychotherapeutic approaches. The following describes the different components of this intervention program.

Construction of the Early Readmission Risk Scale

For the preliminary analysis of risk factors associated with readmission, a retrospective observation will be conducted. This will involve analyzing all episodes from the previous calendar year stored in the database of the MHHU of the RUH of Malaga, provided that the records are complete. "Cases" will be selected from episodes that resulted in readmission within 30 days post-discharge, while an equivalent number of "controls" will be randomly selected through simple random sampling. Following this analysis, a measurement instrument will be developed to determine the risk of early readmission for all patients admitted to the MHHU.

A literature search was conducted to identify variables that have been associated with readmission and early readmission in other populations. The following variables were selected

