for analysis in the reference population: Sociodemographic factors (sex, age, marital status, legal incapacity, employment status, criminal history, and social functioning), psychiatric history (previous admissions, emergency service visits in the twelve months prior to admission, history of suicide attempts, attendance at community nursing follow-ups in the six months prior to admission, and somatic comorbidity), reasons for admission (presence of hetero- or auto-aggression or deficits in self-care), clinical characteristics (primary diagnosis, substance use, non-adherence to follow-up in the previous 12 months, and non-adherence to treatment up to one month before admission), admission characteristics (urgent or scheduled access route and length of stay), and discharge measures (coordination with referring physician in the CMHU and prescription of depot medication).

During admission to the hospitalization unit, all users must have the aforementioned Early Readmission Risk Scale of the MHHU of the RUH of Malaga administered. This will allow for the classification of patients according to their risk level, establishing defined cutoff points, resulting in three categories: Patients at low risk, medium risk, and high risk. This scale will be completed by the referring physician during the initial assessment interview upon admission to implement the proposed measures for each risk level. Additionally, the referring physician will establish contact with the case management figure responsible for the program for the referral of cases with a score indicative of a high risk of early readmission or patients with early readmission within 30 days post-discharge.

Intervention measures based on the risk of early readmission

For patients classified in the low-risk group, general measures would be applied. For patients in the medium-risk group, reinforced measures would be implemented. Lastly, for patients considered to be in the high-risk group, intensive case management measures would be applied, and if they meet the inclusion criteria, they would be included in the Post-Discharge Group Psychotherapeutic Intervention.

1. General measures

The following measures would be applied to patients with a low risk of readmission:

-Ensure coordination between physicians during admission and a follow-up appointment within 7 days.

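### Does the 6-month frequent-readmission outcome lose events because the plan states neither when the window starts nor when data capture ends?

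*Combined protocol and SAP*

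**What the plan says.** Under Secondary outcome variables, the protocol gives the definition: "Frequent rehospitalization will be assessed as having undergone at least two readmissions within a 6-month follow-up period". The outcome is labelled secondary, and it serves the last of the secondary aims.

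Under Participants and recruitment, the programme-year data are described thus: "data from all hospital admission episodes at MHHU during the 12 months following the implementation of the Discharge Transition Intervention Program will be considered". For the comparison year, "data from all users who have experienced any hospital admission episodes at UHSM in the year prior to the intervention will also be utilized".

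The 30-day outcome does have a start point. In the section on constructing the risk scale, cases "will be selected from episodes that resulted in readmission within 30 days post-discharge".

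The section on ethics approval gives the data source for comparing the study groups: "retrospective clinical data recorded in the unit's electronic records will be used".

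On comparators, the Control group section names two: users of the two other hospitals in the province, and users of the Regional Hospital admitted the year before. Data analysis sets a mixed logistic regression for differences from the control groups, in the plural. The Discussion relies on there being two of them.

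**The concern.** The early-readmission window is tied to discharge and the 6-month window is tied to nothing. The only time span attached to the data is the 12 months after launch. Someone reading the two sections together could conclude that the database closes at month 12. A patient admitted in month 10 would then have at most two months in which to be readmitted twice. The planned logistic model takes a yes/no outcome, and the plan gives no rule for partly observed windows, so such patients would be counted as event-free.

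The loss would be large for this outcome, because two events are needed and the second comes late. The worst case is a previous-year comparison in which the earlier year's windows run on into programme-year records while the programme year's windows are cut. The programme would then look effective when it was not.

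A further doubt is whether frequent readmission is compared with the previous year at all. The Secondary outcome variables section names that comparison explicitly only for early readmission, whose risk in the experimental group "will be compared to the risk of early rehospitalization of admission episodes from the previous year".

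**Working it through.** The plan gives no event count, sample size or power for this outcome, so there is no stated figure to reproduce.

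**Inputs from the protocol (Setting):** mean stay 13.7 days, 838 admissions in 2022 (whole unit, used only for scale).

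**Assumptions:** admissions spread evenly over 365 days; 6 months = 182.5 days from discharge; readmissions in the window Poisson with mean 0.1 to 1.2, with the same rate for all patients or gamma-distributed rates (shape 1, 0.5 or 0.2); timing uniform or front-loaded (cumulative share t^0.6); no programme effect unless stated.

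**1. Ordinary reading.** Index episodes are the admissions of the 12 months. Each is followed for 182.5 days after discharge in the electronic records. Incomplete windows: 0%. The last window closes about 18 months after launch, plus the last stay.

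**2. Counterfactual: extraction stops at month 12.** Share of incomplete windows:
- episodes dated by discharge: 182.5/365 = 0.50, or 0.50 × 838 = 419 episodes;
- episodes dated by admission: (182.5 + 13.7)/365 = 0.54, or 0.5375 × 838 = 450 episodes.

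Share of outcomes missed (second readmission after month 12), by simulation: about 15% to 33% by discharge date and 18% to 37% by admission date. A simple Poisson illustration with the 13.7-day stay agrees:

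| Mean readmissions in 6 months | True share with at least 2 | Observed share | Observed/true |
|---|---|---|---|
| 0.25 | 2.6% | 1.7% | 0.64 |
| 0.5 | 9.0% | 5.8% | 0.64 |
| 1.0 | 26.4% | 17.4% | 0.66 |

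**3. What that loss would do to each contrast.**
- *Concurrent hospitals, same readmission timing:* both groups lose nearly the same share. Precision falls and the ratio barely moves.
- *Concurrent hospitals, different timing:* with equal numbers of readmissions (mean 0.5), front-loaded in the controls and uniform under the programme, the missed shares are about 22–26% and 29–32%. A true ratio of 1.00 would read about (1 − 0.32)/(1 − 0.26) = 0.92 or (1 − 0.29)/(1 − 0.22) = 0.91.
- *Previous year, each year counting only its own readmissions:* both years are cut alike, and the ratio stays about 1.00.
- *Previous year complete, programme year cut:* a true ratio of 1.00 would read 1 − 0.33 = 0.67 to 1 − 0.15 = 0.85 by discharge date, and 1 − 0.37 = 0.63 to 1 − 0.18 = 0.82 by admission date.

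**4. What remains on the ordinary reading.** If the previous year adjoins launch, its later windows run into the programme period. In the simulation both readmissions fall after launch in about 5.5% to 20.2% of previous-year outcomes. With an assumed 30% programme effect on those outcomes, a true ratio of 0.70 reads 0.70/(1 − 0.3 × 0.055) = 0.71 to 0.70/(1 − 0.3 × 0.202) = 0.75. The shift is towards no effect.

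**5. Which reading the text supports.** The 12 months in Participants and recruitment qualify admission episodes; they set no closing date for outcomes. A stated 6-month follow-up already implies observation after the index episode. Discharge is the only start point the protocol uses for readmission. The records are retrospective, so a later extraction needs no extra contact with patients. No section stops capture at month 12.

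**The case for a change.** The best case for acting is that start point, index rule and end of capture decide who counts as an event, and that the design is not randomised. Leaving those choices open until the data are visible weakens a named aim, and two or three sentences would settle them. The omissions are real. The index rule for repeat users is the least settled: the plan speaks of episodes for one year and users for the other, and one person's windows can overlap. It is also true that truncation would not be harmless between concurrent groups if the programme delays readmissions rather than preventing them. That is plausible, since its case management is concentrated in the first month after discharge.

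This supports writing the details down when the data are extracted and applying them alike to all groups and years. It does not show that the plan as written gives a wrong answer. The bias figures all need an extraction that stops at month 12, which the plan does not call for.

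The comparator doubt is weaker still. The previous-year users are named as a control group without limit to one outcome, and the analysis and discussion both speak of control groups in the plural. The natural reading is that both comparators apply to every readmission outcome.

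One could add a sensitivity analysis restricted to previous-year windows that close before launch, set against the same calendar months of the programme year. It would address only the small dilution in step 4. It would keep 46% to 50% of previous-year episodes, so intervals would be about √(1/0.50) = 1.41 to √(1/0.4625) = 1.47 times as wide. It would also keep only the programme's first months, when the 20-session weekly group has run little more than one cycle, and so could understate the programme. Statisticians would differ on whether that is worth having.

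**Conclusion.** No change follows. The protocol leaves out the start of the 6-month window, the index rule for repeat users and the end of data extraction, but the ordinary reading fills the first and last of these without loss: admissions of the 12 months, each followed for six months from discharge in the electronic records. On that reading no window is truncated. The index rule is a routine choice for the analyst, to be made the same way in every group.

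The large figures (50% to 54% of windows incomplete, 15% to 37% of outcomes missed) describe an extraction that the plan does not prescribe. They rest on even admissions and on assumed readmission rates and timing. The effect that does remain is the dilution of a previous-year contrast, about 0.01 to 0.05 on a true ratio of 0.70. It works against the programme, concerns a secondary outcome, and could be removed only by giving up about half of the previous-year episodes. That is a fair trade-off as it stands.
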